### 8.2 Modification of Study Product Administration based on Toxicity

Any changes in ferric citrate dosing will be at the discretion of the study investigators and will occur no more frequent than every 2 weeks. If a patient's absolute iron saturation level increases to greater than 50%, the study medication dose will be reduced by half and iron saturation and ferritin levels will be repeated in two weeks. If the iron saturation level is not improved or phosphorus control is not achievable, then the participant will be removed from the study. If a patient's ferritin level increases to >2000 ng/ml, patient's chart will be reviewed by two study investigator to assess the reason for the ferritin increase, and whether the participant should remain in the study.

### 8.3 Adverse Events Reporting

All Adverse event reporting will follow KPSC clinical trials reporting
guideline per KPSC CT SOP 401, Clinical Trial Regulatory Management.

Reportable Event or Incident	Timeframe to report to IRB
Unanticipated death of a research subject that is determined by the PI to be at least possibly related to the study	Within one business day following discovery and at time of continuing review
Reportable Event or Incident Timeframe to report to IRB Internal Unanticipated Serious Adverse Events that meet the three reporting criteria	Within 10 business days following discovery and at time of continuing review
External Unanticipated Serious Adverse Events that meet the reporting criteria	Within 10 business days following discovery and at time of continuing review
External Unanticipated Serious Adverse Events that do NOT meet the reporting criteria (e.g., IND Safety Reports)	At the time of continuing review
Unanticipated Adverse Device Effect	Within 10 business days following discovery and at time of continuing review

Protocol Version 1.4, dated 26-Jun-2018

Breach	Report to KPSC Privacy Officer and IRB immediately following discovery
Protocol Violations	Within 10 business days following discovery and at time of continuing review
Protocol Deviations	Within 10 business days following discovery and at time of continuing review
New Safety Information (e.g., updated investigators' brochure containing new safety information of which the IRB is not yet aware) that meets the reporting criteria.	Within 10 business days following discovery and at time of continuing review
Emergent modifications to the IRB- approved protocol to protect the safety, rights, or welfare of one or more research participants when there is not time to obtain IRB approval	Within five business days of beginning implementation
Incarceration of research a participant	Within two business days following discovery
Inspection by external regulatory agency,3 e.g., FDA, OHRP, DOT, non-US	Within two business days following discovery

### 8.3.1 Definitions

Adverse Event (AE) is any untoward medical occurrence associated with the use of a drug in humans, whether or not considered drug related.

All adverse events, including those that are reported by the patient spontaneously, those the study investigator observes, and those that the study investigator elicits in response to open-ended questions. Recorded adverse events will be assessed by the study investigator indicating the causal relationship of the event with the study drug and whether it meets the criteria for a Serious Adverse Event.

Some reported adverse drug reactions include diarrhea, constipation, abdominal discomfort, abdominal distension, duodenal ulcer, and nausea.

Serious Adverse Event noted in prior publications included death, duodenal ulcer, congestive heart failure, dialysis access shunt stenosis, and infections.

### 8.3.2 Serious Adverse Event Reporting

SERIOUS ADVERSE EVENT (SAE) is an adverse event or suspected adverse reaction if, in the view the study investigator, it meets one or more of the following criteria:

- Results in death
- Is a life-threatening adverse event (places the subject at immediate risk of death from the event as it occurred)
- Results in inpatient hospitalization or prolongation of existing hospitalization
- Results in a persistent or significant incapacity or substantial disruption of the ability to conduct normal life functions
- An important medical event that may not result in death, be lifethreatening, or require hospitalization may be considered serious when, based upon appropriate medical judgment, the event may jeopardize the patient and may require medical or surgical intervention to prevent one of the outcomes listed in this definition

### 8.3.3 Investigator Reporting: Notifying FDA

Any SAE, including death from any cause, which occurs during the study and is deemed related or possibly related to the study drug, will be reported to the FDA and to Med Watch by the study investigator within 24 hours of detection of the SAE.

Withdrawal from the trial and all therapeutic measures taken will be at the discretion of the Principal Investigator (PI). All SAEs (related or of possible relationship to the study drug) will be followed until satisfactory resolution or until the PI deems the event to be chronic or the subject to be stable.

Any subject experiencing one or more SAEs will receive treatment and follow-up evaluations by the Investigator or will be referred to another appropriate physician for treatment and follow-up. SAEs will be monitored from the time of consent and for up to 14 days after the subject has discontinued study drug.

All adverse events, whether serious or non-serious will be followed until resolution (or stabilization, if applicable) or until the adverse event is determined by the Investigator to be no longer clinically significant.

#### **Reporting of SAE's to Ferric Citrate Drug Manufacturer/Supplier:**

Serious Adverse Events (SAE) which occur in patients receiving ferric citrate, from the time of randomization through and including 14 days after the last administration of the study drug, must be reported to Keryx Biopharmaceuticals within 24 hours of becoming aware of the SAE. The Investigator Sponsor will submit an SAE form to Keryx (available 24 hours/day, 7 days/week) to the following:

Email: PV [contact]

Fax: [name]

### 8.3.4 Investigator Reporting: Notifying KPSC IRB

The study investigator will also notify the KPSC Institutional Review Board (IRB) of any SAE within 10 business days per the KPSC IRB SOP 502, Principal Investigator Reportable Event and Incident Requirements.

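### Section 8.3.4 allows ten business days to notify the IRB of any SAE, but the 8.3 table allows one for an unanticipated, possibly related death, and the protocol does not say which governs

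*Combined protocol and SAP*

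**What the plan says.** Section 8.3 places all adverse event reporting under an institutional "guideline per KPSC CT SOP 401, Clinical Trial Regulatory Management" and follows this with a table of events and IRB deadlines. Two rows matter here.

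- The first is "Unanticipated death of a research subject that is determined by the PI to be at least possibly related to the study". Its deadline is "Within one business day following discovery and at time of continuing review".
- The second is "Internal Unanticipated Serious Adverse Events that meet the three reporting criteria". Its deadline is "Within 10 business days following discovery and at time of continuing review".

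Section 8.3.4, the subsection on notifying the IRB, has the investigator notify the same board "of any SAE within 10 business days per the KPSC IRB SOP 502". It sets no condition on cause or expectedness and makes no exception for death. Section 8.3.2 gives "Results in death" as the first criterion for a serious adverse event.

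Section 17.1 says that reporting follows the IRB guidelines set out earlier, without choosing between the two statements.

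**The concern.** Two parts of section 8.3 give the same board different time limits for the same event, and that event is the gravest one the protocol covers. The subsection that an investigator would naturally consult for IRB notification is 8.3.4, and it carries the longer limit. Someone who follows it in good faith could report a possibly related, unanticipated death on the tenth business day and be in breach of the table.

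What is at stake is how promptly the IRB learns of such a death, and whether the site can show that it kept to its own protocol. The trial's estimates are not at stake.

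**Working it through.** No statistical figure is involved. The check sets the two rules side by side for each kind of internal event.

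**Inputs.** The event rows and deadlines come from the table in section 8.3. The general rule comes from 8.3.4, and the definition of a serious adverse event from 8.3.2.

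**Step 1: does the death row fall under both rules?** Death meets the definition in 8.3.2. Section 8.3.4 covers every serious adverse event. An unanticipated, at least possibly related death is therefore covered by the table and by 8.3.4.

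**Step 2: compare the limits.**

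| Internal event | 8.3 table | 8.3.4 | Result |
|---|---|---|---|
| Unanticipated death, at least possibly related | 1 business day | 10 business days | Limits differ by 10 − 1 = 9 business days |
| Other unanticipated SAE meeting the three criteria | 10 business days | 10 business days | Agree |
| SAE that is anticipated or does not meet the criteria | No row | 10 business days | Table silent; no conflicting deadline |

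**Step 3: does anything else settle it?**

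- Section 17.1 points back to the adverse event section as a whole.
- Neither 8.3 nor 8.3.4 refers to the other, and they cite different procedures (CT SOP 401 and IRB SOP 502).
- The 24-hour reports described under the FDA and manufacturer headings go to other recipients and set no IRB deadline.

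The precedence question is therefore open on the text.

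**The case against.** The strongest reply is that the rules are compatible. Ten business days is an outer limit, and the table sets a tighter one for a named subset. Reporting that subset within one business day meets both, and the usual reading is that a specific rule overrides a general one. This is correct as far as it goes, and it is why the point is minor. It does not remove the point, because the protocol never states that precedence and 8.3.4 read alone permits the later date.

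A reader might also infer several stronger things that the documents do not support.

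- **That every drug-related death has conflicting deadlines.** The one-day row requires the death to be unanticipated. Section 8.3.1 says "Serious Adverse Event noted in prior publications included death, duodenal ulcer, congestive heart failure", so it could be disputed whether a given death qualifies.
- **That the rules contradict each other on scope.** The table's internal row is narrower than 8.3.4, but no row forbids or defers reporting of other internal events. Following 8.3.4 simply reports more. The table's text is also visibly broken at that row, so the absence of a further row is weak evidence.
- **That a large number of hospital admissions would be affected.** The documents give no admission rate, and section 5.3 terminates participants after any serious adverse event, which limits repeat events. No count can be defended.
- **That the IRB is the main outside safety check.** Related or possibly related serious events go to the FDA within 24 hours, and serious events in patients receiving the drug go to the manufacturer within 24 hours. A related death would be known outside the site well before day ten.
- **That one SOP should be dropped, or that the three criteria are wrongly omitted.** Neither SOP is in the documents. The criteria may be set out there, and both citations may be needed.

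**Conclusion.** The point holds for one event. An unanticipated death judged at least possibly related to the study has two IRB deadlines, one and ten business days, and the protocol does not say which prevails. The nine-business-day difference assumes that both limits run from discovery; the table says so, while 8.3.4 names no starting point.

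The difference in scope between 8.3.4 and the table's internal row is an ambiguity worth clearing up in the same edit, not a second contradiction. Which section matches the institution's procedures cannot be determined from the documents.

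The issue is minor. It affects no endpoint, analysis or conclusion, but it concerns safety reporting of the most serious outcome and is easily removed.

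**What to change.** Reconcile 8.3 and 8.3.4 against the two cited SOPs. Subject to that check, add one clause to 8.3.4: the ten-business-day limit applies except where the table in 8.3 sets a shorter one, namely one business day for an unanticipated death that is at least possibly related to the study.

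In the same edit, state which text defines the internal events that go to the IRB: every serious adverse event, as in 8.3.4, or only unanticipated ones that meet the three criteria, as in the table.

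The cost is a sentence or two in a protocol amendment, a reading of the two SOPs, and the usual submission of the change to the IRB. No new data, visits or staff are needed.

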### 8.3.3 Time Period and Frequency for Event Assessment and Follow-up

Adverse events are collected on a weekly basis for the in center hemodialysis patients, and on a bi-monthly basis from the home dialysis patients, and again 30days after the termination of the study.

### **9 STUDY SCHEDULE: CLINICAL/ LABORATORY EVALUATIONS**

9.1 Study Schedule

### 9.1.1 Screening Visit

Screening visit will occur during the participant's routine monthly dialysis follow up visit by the participant's nephrologist. Patients who meet the inclusion criteria based on chart review by the study coordinator will be approached and

offered to discuss the study in an opt-in fashion introduced by the patient's nephrologist.

Obtain and document consent from potential patient

- Review medical history to determine preliminary eligibility based on protocol eligibility criteria
- Obtain comprehensive medical history and limited physical exam from the medical history, supplemented by information from the patient
- Assign participant a study ID
- Collect blood specimens for aluminum level

### 9.1.2 Recording of baseline data

A baseline assessment of patient's compliance with usual medications will be performed.

The study coordinator will then review previously obtained routine monthly laboratory values from the dialysis unit, including complete blood count, iron saturation, ferritin, phosphorus, calcium, parathyroid hormone (a total of 6 months of previous data to be reviewed). The study coordinator will then use this baseline data to help determine a patient's eligibility for participation in the active portion of the study, based on the criteria listed in section 5.1. After it is determined that patient actually qualifies for participation in the study, the following will be recorded by the study coordinator:

- Patient's average weekly IV iron and erythropoiesis stimulating agent use (6 months of retrospective data)
- 6 months of retrospective routine laboratory data (CBC, iron saturation, ferritin, calcium, phosphorus, albumin, intact parathyroid hormone levels) will be recorded for each of the previous 6 calendar months
- 6 months of retrospective data regarding medication use will be recorded for each of the previous 6 calendar months (including calcitriol or other vitamin D analogs, cinacalcet, and phosphorus binders), including frequency and dose

After baseline data is obtained, participants will be dispensed a 1 month supply of the study medication, with the starting dose of 1-2 tablets per meal, three times a day. This will mark the start of the active study drug phase.

### 9.1.3 Study phase monthly visit 1-5 (V1, V2, V3, V4, V5) ± 14 days

Participants will be evaluated in person by the study coordinator on a monthly visit, during the same visit when the subject is seen by his/her dialysis provider. Study records will be updated with the following:

- Limited physical exam from the dialysis provider's notes
- Updates in medical history
- Monthly routine dialysis laboratory values from the dialysis unit, including complete blood count, iron saturation, ferritin, phosphorus, calcium, parathyroid hormone
- Provide blood test tube to draw monthly aluminum level
- Update patient's IV iron and erythropoiesis stimulating agent use.
- Assess for study medication compliance via pill counting
- Dispense study medication supply for the following month
- Assess for adverse events

## 9.1.4 Lab draw 2 weeks and 6 weeks into the study (L0.5, L1.5) with optional visit ± 7 days

Participant will have lab draw 2 weeks into the study, and possibly again 6 weeks into the study (if deemed necessary by the study investigator), in between their routine monthly labs, to help adjust the study drug dose to control the serum phosphorus level.

- Collect blood specimens at dialysis unit for complete blood count, iron saturation, ferritin, phosphorus, calcium
- Study coordinator will review laboratory tests with study investigator to assess if study drug dose adjustment is needed.
- Optional visit by study coordinator with the patient to review study medication dosage change

### 9.1.5 Weekly in-center & bi-monthly home dialysis follow up ± 7 days

Participants who are in center dialysis patients will be visited by the study coordinator once a week for pill count and adverse side effect evaluation. Participants who are home dialysis patients will have bi-monthly telephone follow up by the study coordinator to assess medication compliance and adverse side effect evaluation.

### 9.1.4 Withdrawal/ Final Visit (V6) ± 14 days

At end of 6 months of study drug use, or patient's withdrawal from the study, study coordinator will perform the following:

- Update comprehensive medical history
- Update limited physical exam from dialysis provider's note
- Update medical history from health records
- Collect blood specimens for aluminum level test
- Adverse event assessment
- Update laboratory values from the dialysis unit, including complete blood count, iron saturation, ferritin, phosphorus, calcium, parathyroid hormone
- Update patient's average weekly IV iron and erythropoiesis stimulating agent use.
- Perform final pill count to assess medication compliance
- Collect unused investigational product from patient who withdrew from the study
- Record patient preference for oral phosphorus binder at the end of study.

Any participant who wishes to continue with the study drug as their oral phosphorus binder of choice will be provided a prescription for Ferric Citrate. Participants who wish to return to their previous phosphorus binder will be returned to their original binder.

### 9.1.5 30 day post study termination follow-up ± 14 days

Study coordinator will follow up with each participant 30 days after termination or study by patient withdrawal or study completion. Following assessment will be completed:

- Adverse event assessment
- Laboratory values from patient's dialysis unit on complete blood count, iron saturation, ferritin, phosphorus, calcium

#### 9.2 Clinical Evaluations

**Laboratory testing will include**: complete blood count, iron saturation, ferritin, phosphorus, calcium, parathyroid hormone, and aluminum level

**Symptoms evaluation will include**: any hospitalizations, infections, GI bleed, dialysis access complications, diarrhea, constipation, abdominal discomfort, abdominal distension, duodenal ulcer, nausea, and stool color changes.

9.3 Laboratory Evaluations

Routine dialysis laboratory values will be collected from the patient's dialysis unit on a monthly basis per current standard of care. At week 2 and week 6, additional complete blood count, iron saturation, and ferritin levels will be collected at the patient's dialysis unit. Six aluminum levels will be drawn for each participant over the course of the study. Aluminum level tests will be collected in a single vial (royal blue top tube, approximately 4 ml of blood) by the study coordinator and transported on ice to the LAMC laboratory.

9.4	Study Calendar
-----	----------------

Study Procedures	Screening	Baseline Data to be collected	Study phase monthly Visit # 1-5, V1-V5 	Laboratory on week 2 and week 6 	weekly in-center & bi-monthly home dialysis follow up	End of Treatment	30 post follow up
Signed Consent Form	X 4						
Assessment of Eligibility	Х	Х					
Comprehensive History	Х					Х	
Limited Physical Exam	Х		Х			Х	
Update Medical History		Х	Х			Х	
Complete Blood Count	Х	Х	Х	Х		Х	
Iron saturation	Х	Х	Х	Х		Х	
Ferritin	Х	Х	Х	Х		Х	
Phosphorus	Х	Х	Х	Х		Х	
Calcium	Х	Х	Х	Х		Х	
IV iron use	Х	Х	Х			Х	
Parathyroid Hormone (iPTH)	X	Х	Х			Х	
Aluminum level 			Х				
Mean weekly ESA agent dose	Х	Х	Х			Х	
Medication dispensed			Х				
Medication compliance update			X		X	X	
Adverse Event Assessment		X	Х		Х	Х	Х

- 1 Each visit will correspond with monthly hemodialysis or peritoneal dialysis monthly laboratory result round
- 2 Blood test will be drawn during routine hemodialysis. Home dialysis patients will be asked to go to any KPSC laboratory (normal routine for these patients).
- 3 Aluminum level blood tube will be brought by study coordinator to be drawn at hemodialysis with the patient's regular monthly labs. Aluminum test tube will be transported on ice to the LAMC laboratory. Home dialysis patients will be referred to any KPSC laboratory for aluminum testing, when needed.
- 4 Screening visit: If study staff is unable to meet with patient during routine visit or if the patient requests more time to consider participation, peritoneal dialysis patients may be asked to return to clinic for an additional visit to sign the informed consent. This will only apply to peritoneal dialysis patients.

### **10 CRITERIA FOR EVALUATION AND ENDPOINT DEFINITIONS**

### 10.1 Primary Endpoints

Mean serum phosphorus levels and rate of control (<5.5mg/dl) 6 months before and after treatment with ferric citrate, including PTH, calcium, iron saturation, ferritin, hemoglobin and aluminum levels

### 10.2 Secondary Endpoints

- i. Total cumulative and average weekly dose, number of doses of iv iron administered before and after treatment with ferric citrate
- ii. Total ESA dose and mean weekly dose administered 6 months before and after ferric citrate treatment
- Total dose of ferric citrate and average number of pills/day required to maintain phosphorus control compared to previous dose and pill burden with binder
- iv. Compare serious adverse events including tolerability of ferric citrate compared to previous binder

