### **3 STUDY DESIGN**

- Type: non-randomized, single arm, phase IV, cohort pilot study
- Study population: end stage renal disease patients who are on chronic hemodialysis or peritoneal dialysis with elevated serum phosphorus.
- 55 chronic dialysis patients (28 hemodialysis and 27 peritoneal dialysis) who are currently using oral phosphorus binders will be enrolled. Potential participants will be screened from both the chronic hemodialysis unit and the home dialysis unit at the LAMC site. Potential study patients will be approached by study investigators during any routine visit. If the patient consents to participation, the study coordinator will see patients during the same visit. If study staff is unable to meet with patient during routine visit or if the patient requests more time to consider participation, peritoneal dialysis patients may be asked to return to clinic for an additional visit to sign the informed consent. This will only apply to peritoneal dialysis patients. If the patient chooses not to enter the study, the reason will be noted by the study coordinator. At the appropriate time in the study, the study coordinator will dispense the study medication, Ferric Citrate, and provide instructions per study protocol. The study coordinator will meet with the participant every month during either a hemodialysis visit (for hemodialysis patients) or a monthly clinic visit (for peritoneal dialysis patients) with his/her provider, and laboratory values/data and study questionnaire will be updated each month. If at any time during the study, a peritoneal, dialysis patient changes to hemodialysis, the patient can continue study at the principal investigator's discretion. If at any time during the study, a hemodialysis patient changes dialysis to peritoneal, the patient can continue on study at the principal investigator's discretion. In such event, patient's group assignment for analysis will be determined at the discretion of the Principal Investigator. Patients will be allowed to continue in the trial given that they can continue to meet all study participation requirements. The six month period prior to enrollment will be used to evaluate the

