7.2 Criteria for Removal from Treatment

7.2. 1 After six months of study drug use, the study drug will no longer be provided by Keryx free of charge. Patients may continue with Ferric Citrate as their oral phosphorus binder of choice, if desired (at their own expense).

7.2.2 Patients will discontinue treatment in the event of iron overload or any serious adverse side effect deemed attributable or possibly attributable to the study drug.

7.2.3 Patient will be removed if he/she misses the medication continuously for more than 2 weeks.

7.2.4 A patient will be removed from treatment if he/she receives a renal transplant.

7.2.5 Patient will be removed from the study if consent is withdrawn or patient is lost to follow up.

7.2.6 At the discretion of the principal investigator, a patient may be removed from study if they initiate dialysis care at an outside/Non-Kaiser Permanente facility.

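### Total ESA dose, total IV iron dose and the IV iron dose count (10.2 i–ii) shrink with early removal, and the weekly-mean denominator that would avoid this is not stated

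*Combined protocol and SAP*

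**What the plan says.** Two secondary endpoints in Section 10.2 compare anaemia treatment before and after conversion. Item i covers IV iron: "Total cumulative and average weekly dose, number of doses of iv iron administered before and after treatment with ferric citrate". Item ii covers ESA: "Total ESA dose and mean weekly dose administered 6 months before and after ferric citrate treatment". Each gives a total and a weekly figure. The IV iron count has no per-time version.

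The period before conversion is six months. Section 3 says "The six month period prior to enrollment will be used to evaluate the" baseline laboratory values and medication use, and Section 9.1.2 records "Patient's average weekly IV iron and erythropoiesis stimulating agent use (6 months of retrospective data").

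The period after conversion is planned as six months on drug (Sections 3.1 and 3.2), but the final data-collection visit in Section 9.1.4 (Withdrawal/Final Visit) takes place "At end of 6 months of study drug use, or patient's withdrawal from the study". The 30-day follow-up after termination lists only adverse events and laboratory values. In the Section 9.4 calendar, the IV iron and ESA rows are blank in the follow-up column.

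There are several routes to early removal. Section 7.2.3 states "Patient will be removed if he/she misses the medication continuously for more than 2 weeks". Section 5.3 adds serious adverse events, loss to follow-up, transplantation and pregnancy. The rest of 7.2 adds iron overload, withdrawn consent and a possible move to outside dialysis care. Section 8.2 adds iron saturation that does not improve and phosphorus that cannot be controlled.

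Section 14.4, the final analysis plan, is marked not applicable.

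**The concern.** A total is a rate multiplied by observation time. If the period before conversion is six months and the period after is shorter for some patients, the total after conversion is lower for those patients whatever the drug does. The same holds for a count of doses.

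The error runs in one direction. The more patients leave ferric citrate early, the larger the apparent reduction in ESA and IV iron. Aims 4 and 6 in Section 2 ask about iron and ESA requirements after conversion, so poor tolerability could read as a benefit on those aims. With no analysis plan, nothing says which of the total and the weekly mean is the main measure, what the weekly mean is divided by, or how removed patients enter the comparison.

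**Working it through.** The plan has no figure to reproduce: Sections 14.2 and 14.4 are marked not applicable, and no attrition rate is given.

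**Inputs from the documents**
- Period before: 6 months, taken as 26 weeks (Sections 3 and 9.1.2).
- Planned period after: 6 months, 26 weeks (Sections 3.1 and 3.2).
- End of dose collection: 6 months or withdrawal (Section 9.1.4, Withdrawal/Final Visit), with none listed later (30-day follow-up; Section 9.4).
- Patients: 55 (Section 3).

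**Assumptions**
- Share removed early, *d*: 0–40%.
- Mean week of removal, *t*: 6.5, 13 or 19.5.
- Weekly use *w* is the same before and after, and on average the same in patients who leave and patients who stay. This is a benchmark for no change, not a forecast.

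**Step 1: one patient.** Total before = 26*w*; total after = *t·w*; change = *t*/26 − 1.
- Removed at week 8: 8/26 − 1 = −69%.
- Week 13: −50%.
- Week 20: −23%.
- Week 26: 0%.

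**Step 2: the cohort.** Change in mean total = −*d*(1 − *t*/26).

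| Removed early | Mean week 6.5 | Mean week 13 | Mean week 19.5 |
|---|---|---|---|
| 0% | 0% | 0% | 0% |
| 10% (5.5 of 55) | −7.5% | −5% | −2.5% |
| 20% (11 of 55) | −15% | −10% | −5% |
| 30% (16.5 of 55) | −22.5% | −15% | −7.5% |
| 40% (22 of 55) | −30% | −20% | −10% |

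For removal at a mean of 3 months (week 13), 0.10 × 0.5 = 5% and 0.30 × 0.5 = 15%. The IV iron count behaves in the same way if the frequency of dosing is unchanged.

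**Step 3: the weekly mean under two divisors.**
- Weeks actually observed: *t·w*/*t* = *w*, a change of 0% at any removal rate.
- Fixed 26 weeks: *t·w*/26, the same fall as the total in Steps 1 and 2.

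**Step 4: what the totals could hide.** If weekly use changes by the same ratio in everyone, the observed ratio of totals = true ratio × [1 − *d*(1 − *t*/26)].
- 20% removed at mean week 13: factor 0.90, so a true rise of 1/0.90 − 1 = 11.1% would show as no change.
- 30% removed at mean week 13: factor 0.85, so a true rise of 1/0.85 − 1 = 17.6% would show as no change.

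**The case against.** The strongest reply is that the plan already lists the right measure. Items i and ii each include a weekly dose, and Sections 9.1.2 and 9.1.4 collect ESA and IV iron as weekly averages. A reader might infer that these drugs are compared only as totals; the text does not support that. What stands against the reply is narrower: the totals and the IV iron count remain named before/after endpoints, the count has no per-time partner, and the weekly divisor is undefined.

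A second reply is that the wording of item ii could mean a fixed six months after conversion, with medical records (a named source in Section 12.1) filling the gap. That is possible, and the cut-off at removal is inferred from the visit schedule rather than set as an analysis rule. But no dose collection after removal is listed, and a fixed window would mix time off the drug into the period after conversion. Restricting totals to completers would also remove the window-length bias; the plan does not say that this will be done.

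Third, the study is an unpowered pilot with a feasibility aim. That lowers the importance of the point. It does not remove a directional bias in a descriptive estimate.

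Four further inferences are tempting and should not be drawn:
- **The binder endpoint has the same fault.** Item iii reads "Total dose of ferric citrate and average number of pills/day required to maintain phosphorus control compared to previous dose and pill burden with binder". It compares with a previous dose and pill burden, not expressly with a six-month total, and it includes pills per day.
- **The ±14-day tolerance on the final visit adds to the fall.** It can move a total by up to about 8% (2/26 weeks = 7.7%) in either direction. That is noise, not a reduction.
- **Every patient has a full six months before conversion.** This is the design intent, but no criterion requires six months of prior dialysis or ESA use.
- **The more favourable version will be chosen for reporting.** Both are listed endpoints, and nothing in the documents suggests selective reporting.

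**Conclusion.** The point holds for total IV iron dose, the number of IV iron doses and total ESA dose in 10.2 i and ii. As scheduled, these fall mechanically when patients leave early. The fall is about 5–15% if 10–30% leave at a mean of 3 months, and zero if nobody leaves. These attrition figures are assumptions, and the result also assumes similar weekly use in patients who leave and patients who stay. The weekly means are free of the window-length bias only with observed weeks as the divisor, which the plan does not state.

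A reader might go further and conclude that any reported ESA or IV iron saving would be an artefact of attrition. The documents do not support that: they give no attrition rate, and a correctly defined weekly mean would show a real change. Severity is minor.

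**What to change.** In 10.2 i and ii, make dose per week the before/after comparison, defined as dose given divided by weeks actually observed in each period. Give IV iron administrations as doses per patient-month observed. Report totals descriptively beside weeks observed, or only for patients with the full six months in both periods.

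The cost is mainly wording. Weekly averages are already collected at baseline and at the final visit. IV iron administrations are not listed explicitly in either place, so the data form should capture their number, which item i needs in any case, together with the weeks observed in each period.

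Two limits should be stated. The before/after contrast in total dose saved is lost as a headline. Rates also correct only for length of observation: if patients are removed for reasons linked to their iron or ESA needs, that selection remains, so completers and removed patients should also be shown separately.
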